UM IRB No.: 20211211

NCT05545735

Protocol Date: November 14, 2023

Principal Investigator: [name]., M.S.P.H.

Study Title: The Duration of Antibiotic Therapy for Early VAP (DATE) Trial

Cover Page for Protocol

Sponsor name:	None
ClinicalTrials.gov ID#	NCT05545735
University of Miami IRB#	20211211
Brief title:	The Duration of Antibiotic Therapy for Early VAP (DATE) Trial
Official title of study:	The Duration of Antibiotic Therapy for Early VAP (DATE) Trial: A Surgical Infection Society Multicenter Randomized Clinical Trial of 4 vs. 7 Days of Definitive Antibiotic Therapy for Early Ventilator-Associated Pneumonia in the Surgical Intensive Care Unit
Document date:	November 14, 2023

UM IRB No.: 20211211

NCT05545735

Protocol Date: November 14, 2023

Principal Investigator: [name]., M.S.P.H.

Study Title: The Duration of Antibiotic Therapy for Early VAP (DATE) Trial

I. Protocol Title

The Duration of Antibiotic Therapy for Early VAP (DATE) Trial: A Surgical Infection Society Multicenter Randomized Clinical Trial of 4 vs. 7 Days of Definitive Antibiotic Therapy for Early Ventilator-Associated Pneumonia in the Surgical Intensive Care Unit

II. IRB Review History

Not applicable

III. Hypothesis and Specific Aims

The **hypothesis** of this randomized controlled trial (RCT) is that 4 days of antibiotic therapy, as compared to 7 days, is non-inferior regarding the primary outcome of ventilator-associated pneumonia (VAP) recurrence and superior in decreased antibiotic exposure among surgical intensive care unit (ICU) patients with early (within 2 – 7 days of intubation via endotracheal or tracheostomy tube) VAP. Our **specific aim** is to determine whether 4 days of antibiotic therapy is non-inferior to 7 days of antibiotic therapy for the treatment of early VAP with regards to recurrence and superior with regards to antibiotic exposure time.

IV. Background

The prevalence of multidrug resistant (MDR) pathogens in ICUs worldwide has reached epidemic proportions (1, 2). In some cases, the choice of potential therapy is limited or even nonexistent (3). Antibiotic prescription, through selection pressure, represents the main mechanism by which resistance emerges (4). Limitations in the development of new antibiotics (5) underscores the importance of adherence to the principles of antibiotic stewardship (6).

VAP is the most common serious infection in mechanically ventilated critically ill patients (7). Approximately one half of antibiotic prescription in the ICU is related to VAP, including prophylactic, empiric, and definitive therapy (8). The development of evidence-based

UM IRB No.: 20211211

NCT05545735

Protocol Date: November 14, 2023

Principal Investigator: [name]., M.S.P.H.

Study Title: The Duration of Antibiotic Therapy for Early VAP (DATE) Trial

algorithms for the rational use of antibiotics in the management of patients with both suspected and confirmed VAP is pivotal to decreasing the emergence of MDR pathogens.

Shortening the duration of antimicrobial therapy for VAP represents one strategy to curtail the emergence of MDR pathogens. Although prior guidelines recommended a treatment course of 8 – 14 days (9), newer guidelines recommend a treatment course of 7 days (10, 11) and data show that both clinical and microbiological resolution of infection typically occur much sooner (12, 13). In one study of ICU patients ventilated for > 5 days who developed VAP, 8 days of antimicrobial therapy was equally as effective as 15 days, provided VAP was not caused by a non-lactose fermenting gram negative bacillus (14). Favorable results following courses of therapy < 8 days have been reported, albeit in small uncontrolled series (15).

One subset of patients for whom a decreased duration of antimicrobial therapy may be particularly effective is those who develop VAP \leq 7 days after intubation (i.e., early VAP). Early VAP comprises the majority of cases of pneumonia diagnosed in the ICU (16). Furthermore, as compared to patients who develop late VAP, patients who develop early VAP are more likely to be infected with community-acquired pathogens sensitive to narrow spectrum antibiotics (16).

Finally, nearly all cases of early VAP caused by sensitive pathogens demonstrate microbiological resolution after relatively short (i.e., 3 – 5 day) courses of therapy (12). Therefore, we have designed this multicenter randomized controlled trial in partnership with the Surgical Infection Society to determine whether a shorter course of antibiotic therapy (i.e., 4 days) is non-inferior as longer therapy (i.e., 7 days) for the treatment of early VAP in critically ill surgical patients regarding recurrences and superior regarding antibiotic exposure.

UM IRB No.: 20211211

NCT05545735

Protocol Date: November 14, 2023

Principal Investigator: [name]., M.S.P.H.

Study Title: The Duration of Antibiotic Therapy for Early VAP (DATE) Trial

V. Inclusion and Exclusion Criteria

A) Inclusion Criteria

- a.** Surgical patient
- b.** Early VAP, defined as VAP occurring within 2 – 7 days of intubation (via endotracheal or tracheostomy tube) (9). VAP will be defined according to local institutional protocol.
- c.** Hospital length of stay (LOS) \leq 10 days at the time of VAP diagnosis.
- d.** Patients are willing to provide informed consent or their Legally Authorized Representative (LAR) is willing to provide informed consent on their behalf when the patient is unable (i.e., cognitively impaired from sedation on a ventilator).

B) Exclusion Criteria

- a.** Age $<$ 18 years
- b.** Prior episode of VAP for the index admission
- c.** VAP caused by any of the following pathogens:
 - i.** Methicillin-resistant *Staphylococcus aureus* (MRSA)
 - ii.** Vancomycin-intermediate *Staphylococcus aureus* (VISA)
 - iii.** *Pseudomonas aeruginosa*
 - iv.** Vancomycin-resistant *Enterococcus* (VRE)
 - v.** *Acinetobacter baumanii*
 - vi.** *Stenotrophomonas maltophilia*
 - vii.** Carbapenem-resistant *Enterobacteriaceae* (CRE)
 - viii.** Extended-spectrum beta lactamase-producing gram-negative bacilli
- d.** Causative pathogen not sensitive to choice of initial empiric antibiotic
- e.** Antibiotic therapy for \geq 5 of the last 10 days preceding VAP diagnosis
- f.** Septic shock, defined as evidence of tissue hypoperfusion after adequate volume expansion, due to infection, and requiring \geq 1 vasopressor (17)

UM IRB No.: 20211211

NCT05545735

Protocol Date: November 14, 2023

Principal Investigator: [name]., M.S.P.H.

Study Title: The Duration of Antibiotic Therapy for Early VAP (DATE) Trial

- g.** Current or recent (within 30 days) use of immunosuppressive medications
- h.** LOS \geq 72 hours at a transferring facility
- i.** Pregnancy or lactation
- j.** Legal arrest or incarceration
- k.** Moribund state in which death is imminent
- l.** ECMO (Extracorporeal membrane oxygenation)
- m.** Extubation prior to randomization

VI. Number of Subjects

The total required sample size for this study is **458 patients**. Assumptions for the power analysis include non-inferiority for VAP recurrence and superiority for antibiotic-free days in the intervention group, 3 planned analyses of the data with O'Brien-Fleming spending function with binding futility boundaries, 25% recurrence rate in the control group (14), and 6 enrolling centers with an average cluster size of 10. To detect a 10% difference in outcomes between groups with 80% power and assuming a 10% dropout rate, a total sample size of 458 patients is required for this study. Sample size will be recalculated at each interim analysis with better estimates based on accrued patients. The planned analyses will take place after enrollment of 150, 300, and all patients.

VII. Study-Wide Recruitment Methods

This is a multicenter randomized controlled trial. We have partnered with the Surgical Infection Society to aid in recruitment of interested centers for participation in the study. The recruitment methods for individual subjects to participate in the study will be uniform across all centers. A member of the research team at each center will screen all patients in their respective surgical ICUs by reviewing the medical record of each patient in the ICU for eligibility based on the inclusion and exclusion criteria listed in *Section V* (above). Screening will occur daily during the study period. We will be requesting a waiver of the requirement for written authorization

UM IRB No.: 20211211

NCT05545735

Protocol Date: November 14, 2023

Principal Investigator: [name]., M.S.P.H.

Study Title: The Duration of Antibiotic Therapy for Early VAP (DATE) Trial

from patients to access their health records due to the nature of the study. Please see further documentation in *Section XXXII* (below).

VIII. Study Timeline

Each individual patient enrolled in the study will be followed for 30 days or until hospital discharge, whichever occurs first. We will also review patient charts at hospital discharge to determine overall hospital length of stay and overall mortality, in addition to 30-day outcomes. We expect all subjects to be enrolled within the first 2 years of study across all centers, with full data analysis completed at 3 months after study completion.

IX. Study Endpoints

A) Primary Outcomes

- a.** VAP recurrence within 30 days
 - i.** VAP recurrence = VAP occurring 2 – 14 days following completion of initial therapy
- b.** Antibiotic-free days within 30 days

B) Secondary Outcomes

- a.** Antibiotic exposure
 - i.** Days of antibiotics
 - ii.** Antibiotic days (defined as the product of days of antibiotics and number of antibiotics per day)
- b.** Clinical improvement, measured using daily CPIS_{clinical} score while enrolled in the study
- c.** VAP relapse = recurrent VAP caused by initial pathogen (if culture data available), occurring 2 – 14 days following completion of initial therapy
- d.** 30-day Ventilator-free days

UM IRB No.: 20211211

NCT05545735

Protocol Date: November 14, 2023

Principal Investigator: [name]., M.S.P.H.

Study Title: The Duration of Antibiotic Therapy for Early VAP (DATE) Trial

- e. Empyema
- f. Need for tracheostomy
- g. Non-pulmonary infections
- h. 30-day ICU-free days
- i. Hospital LOS
- j. In-hospital Mortality

X. Procedures Involved

This is a multicenter, randomized, clinical trial. The trial will be reported in accordance with the recommendations of the CONSORT statement (18). IRB approval will be obtained. All subjects, or their legally authorized representatives, will provide written consent for study participation. The trial is registered with the US National Institutes of Health (ClinicalTrials.gov Identifier #NCT05545735).

Screening will occur daily by study personnel. Eligible patients will be approached as soon as possible after inclusion criteria are met (i.e., 1 – 3 days prior to randomization). Randomization will occur using a computer-generated block pattern no later than the end of the fourth day of appropriate antibiotic therapy. Randomization will occur at the hospital level in blocks of 20.

Empiric antibiotic therapy will be instituted as soon as possible following diagnosis of suspected pneumonia by the clinical team. The default antibiotic will be based on the local institutional antibiogram and practice. Pre-existing treatment for a non-pulmonary infection with at least one antibiotic that has appropriate activity against the VAP pathogen may be substituted for the default antibiotic. Once sensitivity data become available, therapy may be de-escalated to a more narrow-spectrum agent, as indicated.

The default duration of antibiotic therapy will be determined by study group assignment; the treatment team will be asked to adhere to study group assignment whenever possible. However, the treatment team may choose to extend the duration of antibiotic therapy based on

UM IRB No.: 20211211

NCT05545735

Protocol Date: November 14, 2023

Principal Investigator: [name]., M.S.P.H.

Study Title: The Duration of Antibiotic Therapy for Early VAP (DATE) Trial

clinical circumstances, such as deterioration in hemodynamic or respiratory status that is believed to be related to incompletely treated VAP, or continued treatment of a non-pulmonary infection. The treatment team may also decide to extend the duration of antibiotic therapy based on the results of procalcitonin measurements, if obtained. Clinical decisions will take precedence over study group assignment.

Patients will be followed for 30 days or until hospital discharge, whichever occurs first. Please see the attached data collection tool for detailed information.

Adverse event monitoring will occur daily at each individual institution. Any adverse event will trigger notification to the site PI per local IRB regulations. The safety of the study will be monitored by an independent Data Safety Monitoring Board (DSMB). The DSMB has been formed by the Surgical Infection Society and will consist of Drs. [name], [name], and [name]. The committee will meet after each planned interim analysis (see *Sections VI and XII*) and submit a written report to the overall study PI ([name]), who will submit to the IRB (see attached “*DSMB Charter*”).

Disease Related Adverse Events: It is recognized that this patient population who require critical care support will experience a number of common aberrations in laboratory values, signs, and symptoms due to the severity of the underlying disease and the impact of standard therapies. These will not necessarily constitute an AE unless they:

- require significant intervention,
- lead to discontinuation of study procedures,
- felt to be related to study procedures
- or are considered to be of concern, in the Investigator’s clinical judgment.

Examples of the type of AEs that may be associated with the patient population are acute respiratory failure; respiratory distress; acute lung injury; acute respiratory distress syndrome (ARDS); acute renal failure; fever, bacteremia; sepsis, septic shock; hypotension; metabolic acidosis, pleural effusion; mineral or electrolyte imbalance. For purposes of this study, deaths

UM IRB No.: 20211211

NCT05545735

Protocol Date: November 14, 2023

Principal Investigator: [name]., M.S.P.H.

Study Title: The Duration of Antibiotic Therapy for Early VAP (DATE) Trial

will be captured as clinical outcomes and do not need to be reported as SAEs unless felt related to study procedures.

XI. Data and Specimen Banking

There will be no specimen banking for this study.

XII. Data Management

All data will be collected on the attached case report form (CRF) and then input by study personnel at each individual site into the University of Miami REDCap electronic data management system. Each site PI will be responsible for keeping a secure file linking the patient medical record number (MRN) to their study ID in the event that additional information is required for study analysis, which will be destroyed at the conclusion of the study. All data will be entered into REDCap in a de-identified manner, using only the study ID, without including any personal identifying information. Data analysis will be performed by [name], PhD. [name] is a tenured Professor of Surgery and Public Health at the University of Colorado Denver and the Colorado School of Public Health, where she is also the Associate Director of the NIH-funded T32 postdoctoral research fellowship in trauma surgery, and statistical consultant to the Ernest E. Moore Shock Trauma Center at Denver Health Medical Center. Additionally, she is the former Statistical Editor for the *Journal of Trauma and Acute Care Surgery*, with over 30 years' experience in injury-related research, particularly in critically ill and injured patients.

Three equally spaced analyses (two interim and one final) will be conducted for all outcomes, using the O'Brien-Fleming alpha spending function. Data analyses will be performed using SAS v9.4 (SAS Inc., Cary, NC). Randomization will occur at the hospital level in blocks of 20. Data will be analyzed using an intention-to-treat strategy (i.e., data of patients randomized to receive 4 days of antibiotic therapy will be analyzed as belonging to this group even if they receive longer courses) and a per-protocol strategy (i.e., crossovers and protocol violations

UM IRB No.: 20211211

NCT05545735

Protocol Date: November 14, 2023

Principal Investigator: [name]., M.S.P.H.

Study Title: The Duration of Antibiotic Therapy for Early VAP (DATE) Trial

excluded). Data will be expressed as median (interquartile range) or frequency (%). Normality of continuous variables will be assessed by visual inspection of histograms. Differences in the means of continuous normally distributed variables will be assessed using Student's t-test or ANOVA. Differences in the medians of non-normally distributed continuous variables will be assessed using the Wilcoxon rank sum or Kruskal-Wallis tests. Proportions will be compared using the chi-squared or Fischer's exact test, as appropriate. Univariate analysis of categorical outcomes will be expressed as the relative risk with 95% confidence intervals, with standard errors adjusted for intra-center clustering. A generalized estimating equation or linear mixed model (with appropriate transformation of outcome variables to approximate normality, if needed) will be fit to address possible confounding if randomization fails to assure equitable distribution. Baseline variables associated with randomization status at the $p < 0.25$ level by univariate analysis will be added to the model using a stepwise selection method. The overall contribution of the fitted model to predicting variability in the outcome of interest will be assessed using the likelihood ratio chi-squared test. The alpha error level is defined at 0.05, with statistical significance at $p < 0.05$. No adjustment for multiplicity of outcomes will be done as this is an exploratory (rather than confirmatory) trial, and all hypotheses are pre-planned. Adjustment for multiple comparisons in pre-planned hypotheses leads to more type II errors (19, 20).

XIII. Provisions to Monitor the Data to Ensure the Safety of Subjects

As mentioned previously (see *Section X*), a DSMB will be convened. The DSMB will meet after each planned interim analysis, review data collected across all sites, and submit a written report to the overall study PI, who will submit the report to the IRB. Data analysis will be performed by [name], as mentioned above (see *Section XII*).

Data will be monitored daily at each site and any adverse events will be reported to the site PI per local IRB regulations. Efficacy and safety data will be collected on CRFs and inputted into REDCap by study personnel at each site. The study will be terminated early if there are

UM IRB No.: 20211211

NCT05545735

Protocol Date: November 14, 2023

Principal Investigator: [name]., M.S.P.H.

Study Title: The Duration of Antibiotic Therapy for Early VAP (DATE) Trial

unacceptably high rates of adverse events or if there is a clear benefit noted in either study group, as deemed by the DSMB.

XIV. Withdrawal of Subjects

Subjects, or their legally authorized representatives, can withdrawal from the study at any time. If a subject wishes to withdraw from the study, we will request their permission to allow us to continue collecting data to use in the intention-to-treat analysis. As previously mentioned (see *Section X*), the clinical team may choose to continue antibiotic therapy despite the subject's study group allocation. Clinical decision-making will supersede any study procedures or protocols.

XV. Risks to Subjects

There is a risk that a default of 4 days of antibiotic therapy will be too short. In order to mitigate this risk, clinical endpoints will be followed daily during treatment. If any of these endpoints suggest inadequate therapy, the treatment team may choose to extend the duration of treatment. This decision will take precedence over study group assignment.

XVI. Potential Benefits to Subjects

The most significant potential direct benefit to subjects enrolled in this study is the possibility of limiting days of antibiotic exposure. Limiting the number of days receiving antibiotic therapy may decrease the subjects' individual risk of developing *Clostridium difficile* colitis, a common and potentially life-threatening consequence of antibiotic exposure. Similar multicenter randomized controlled trials aimed at limiting antibiotic days in patients with intra-abdominal infections have recently been published, with the University of Miami as a participating center, and have shown a benefit to shorter antimicrobial therapy, including less antibiotic days without increase in infectious complications (21).

UM IRB No.: 20211211

NCT05545735

Protocol Date: November 14, 2023

Principal Investigator: [name]., M.S.P.H.

Study Title: The Duration of Antibiotic Therapy for Early VAP (DATE) Trial

XVII. Vulnerable Populations

Our research does not involve pregnant women, neonates, children, or prisoners. In potential subjects being mechanically ventilated and cognitively impaired, their LAR will be approached to provide informed consent.

XVIII. Multi-Site Research

This is a multicenter randomized controlled trial. The University of Miami will serve as the coordinating center for the study and [name], Assistant Professor of Surgery in the Divisions of Trauma and Surgical Critical Care, DeWitt Daughtry Family Department of Surgery, University of Miami Miller School of Medicine, will serve as the lead investigator. [name], ARNP, MSPH, will serve as the study coordinator.

Prior to enrollment of the first study participant, we will coordinate a meeting of all site PIs and coordinators to review the study protocol and answer any questions. This meeting will occur via a virtual meeting platform (e.g., Zoom). During this meeting, we will ensure that all sites have the current protocol. We will also ensure that all appropriate safeguards are in place, including a location for CRFs to be stored in a locked office. Prior to this meeting, we will ensure that all sites have received IRB approval from their local IRB. We will plan to meet with all sites via virtual meeting platform from 1 – 4 times per month, as appropriate, at which time we will ensure study compliance, timely reporting of adverse events, and answer additional questions. Prior to the implementation of any study modification, we will contact all sites, ensure that the modification has been submitted to their local IRBs, and ensure that approval has been attained from their local IRBs. DSMB reports will be furnished to each site via either email or during one of these study meetings. Any problems with the study and closure of the study will also be reported as outlined above.

XIX. Community-Based Participatory Research

This study does not involve community-based participatory research.

UM IRB No.: 20211211

NCT05545735

Protocol Date: November 14, 2023

Principal Investigator: [name]., M.S.P.H.

Study Title: The Duration of Antibiotic Therapy for Early VAP (DATE) Trial

XX. Sharing of Results with Subjects

Results of the study will not be shared with individual subjects. The findings of the study will be presented at the Annual Scientific Meeting of the Surgical Infection Society and published in a peer-reviewed journal upon study completion.

XXI. Setting

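### The sample size assumes binding futility boundaries, but the sections on interim analysis and stopping contain no futility rule, so the supplied text does not make futility binding

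*Combined protocol and SAP*

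**What the plan says.** Section VI (Number of Subjects) bases the 458 patients on three looks at the data with an "O'Brien-Fleming spending function with binding futility boundaries". It places the looks as follows: "The planned analyses will take place after enrollment of 150, 300, and all patients". It also says that the sample size will be recalculated at each interim.

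Section XII (Data Management) describes the same looks without futility: "Three equally spaced analyses (two interim and one final) will be conducted for all outcomes, using the O'Brien-Fleming alpha spending function".

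Section XIII (Provisions to Monitor the Data) allows early termination for "unacceptably high rates of adverse events or if there is a clear benefit noted in either study group, as deemed by the DSMB". It gives no futility criterion and no numeric boundary, and it does not oblige the DSMB to stop.

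Section X has the DSMB meet after each interim analysis, points to Sections VI and XII for those analyses, and cites an attached DSMB charter. The charter is not among the supplied documents. No supplied section gives a futility boundary value or a beta-spending function.

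**The concern.** Binding is a technical property. In a binding design, a trial that crosses futility is assumed to stop every time, so it can no longer produce a false positive. The design uses that saving to lower the final efficacy boundary. The saving is legitimate only if the stop is in fact compulsory. Here the sizing section relies on a compulsory stop, the analysis section does not mention one, and the stopping section describes a discretionary decision on other grounds.

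Two things are at stake. First, a reader cannot tell which final critical value applies to the primary non-inferiority test. One candidate preserves alpha only if every futility crossing is obeyed. Second, if 4 days really is worse by the full 10 points, the power analysis assumes that most such trials end at an interim look, and the supplied stopping text does not call for that.

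**Working it through.** **Inputs from the protocol.** Three looks at 150, 300 and 458 give information fractions 150/458 = 0.328, 300/458 = 0.655 and 1 (Section VI). Alpha: "The alpha error level is defined at 0.05" (Section XII), sidedness not stated. Section VI gives 25% control recurrence, a 10-point difference, and sizing "with 80% power and assuming a 10% dropout rate".

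**Assumptions.** One-sided 5% and one-sided 2.5% are both computed. Allocation is 1:1, and the 10-point difference is read as the non-inferiority margin. Alpha spending is Lan-DeMets O'Brien-Fleming, α(t) = 2 − 2Φ(z for α/2 ÷ √t). Beta spending has the same form in the base case and is varied over Hwang-Shih-DeCani −4 and −2 and Pocock.

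**Step 1: the plan's own figure.** The fixed-design non-inferiority total is 2 × 2 × 0.25 × 0.75 × (zα + zβ)² ÷ 0.10². Rounded up per arm, it is 464 at one-sided 5% and 590 at 2.5%. Applying the binding-design inflation (1.069 and 1.059) and dividing by 0.9 for dropout gives about 550 and 693, before any clustering. So 458 is not reproduced. Two variants come close: 464 with no looks, dropout or clustering, and 462 to 468 for detecting 25% against 15% at one-sided 5% with looks and dropout. This is a separate matter and affects only how power should be restated.

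**Step 2: boundaries and error rates**, by recursive numerical integration.

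| Quantity | One-sided 5% | One-sided 2.5% |
|---|---|---|
| Binding design, efficacy z at looks 1, 2, 3 | 3.232, 2.163, 1.628 | 3.746, 2.537, 1.931 |
| Binding design, futility z at looks 1, 2 | −0.487, 0.831 | −0.308, 1.084 |
| Final efficacy z when futility is non-binding or absent | 1.692 | 1.991 |
| Type I error, binding boundaries, futility obeyed | 5.0% | 2.5% |
| Type I error, binding boundaries, futility not obeyed | 5.59% | 2.83% |
| Same, range over beta-spending shapes | 5.1-6.4% | 2.6-3.3% |
| Inflation over fixed design: binding / non-binding / efficacy only | 1.069 / 1.118 / 1.019 | 1.059 / 1.101 / 1.012 |

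The not-obeyed error rates were confirmed with 4 million simulated paths. With looks at exact thirds, as Section XII's equal spacing implies, they are 5.61% and 2.84%.

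**Step 3: if 4 days is truly 10 points worse.** The probability of crossing futility by look 2 is 80% (5%) or 87% (2.5%) under O'Brien-Fleming beta spending. Over the four shapes it is 64-85% or 72-90%.

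**Step 4: does a clear-benefit stop for 7 days do the same job?** At look 2, take 300 patients, 25% recurrence and 1:1 allocation. The standard error is √(0.375 ÷ 150) = 0.05. At one-sided 5%, futility is crossed when 4 days looks worse by more than 10 − 0.831 × 5 = 5.8 points. An O'Brien-Fleming superiority stop for 7 days would need 2.163 × 5 = 10.8 points. At 2.5% the figures are 10 − 1.084 × 5 = 4.6 and 2.537 × 5 = 12.7. Between the two values the power analysis treats the trial as finished, while a clear-benefit rule at that threshold would not stop it.

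**Step 5: power at the N that gives 80% with binding boundaries**, O'Brien-Fleming beta spending. With non-binding futility that is nonetheless followed, power is 78.8-78.9%. With efficacy-only boundaries and no futility stop, it is about 82%.

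**The case against.** A reader might infer that the trial's error rate is inflated as it stands. The documents do not support that. Inflation needs two things together: the lowered binding-design boundaries are used at analysis, and the trial continues past futility. Section XII names only alpha spending. If efficacy-only boundaries are what the analyst applies, alpha holds whatever the DSMB does about futility, and power at the planned N is slightly higher than stated, not lower. This part of the objection stands in full.

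A reader might also infer that a failing short course could not be stopped. That goes too far. Section XIII allows a stop for adverse events or for clear benefit in either group, which includes the 7-day group. Such a stop is discretionary and, as Step 4 shows, need not coincide with futility for non-inferiority, but it exists.

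Nor do Sections VI and XIII flatly contradict each other. Section XIII does not call its grounds exhaustive, Section X links the DSMB to Section VI, and the charter may hold the rule. The absence is therefore established only for the supplied text. Even so, a charter rule would leave Sections XII and XIII to be reconciled with Section VI.

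Finally, the sizes rest on an unstated beta-spending function. At the low end the inflation is about 0.1 point, and sample-size recalculation means that the information fractions are not fixed. Hence the ranges.

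**Conclusion.** The concern holds in a limited form. The sample size relies on a property, compulsory stopping for futility, that no supplied section delivers.

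The consequence depends on which boundaries are used. With binding-design boundaries and a trial that runs on past futility, the false non-inferiority rate rises by about 0.6 points at one-sided 5% (0.1 to 1.4 over the shapes examined) or 0.3 points at 2.5% (0.1 to 0.8). With Section XII's boundaries there is no inflation, but the trial analysed differs from the trial powered. If the short course is 10 points worse, the sizing assumes an interim futility stop in roughly two thirds to nine tenths of trials, and Section XIII offers only a discretionary stop on other grounds.

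The effect is modest, and the point should be settled before an interim analysis is acted on. It does not depend on whether 458 can be reproduced.

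**What to change.** In Sections VI and XII, state that the efficacy boundaries are computed ignoring futility (non-binding), with final z about 1.69 at one-sided 5% or 1.99 at one-sided 2.5%. Say which alpha level applies and name the beta-spending function. Keep 458.

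Restate the power from the trial's actual inputs. Subtracting 1.2 points from 80% would be wrong, because 458 does not reproduce 80% for a non-inferiority design. With 458 × 0.9 ≈ 412 evaluable patients, 25% recurrence in both arms, a 10-point margin, and no clustering or interim looks, power is about 76% at one-sided 5% or 65% at 2.5%.

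Reconcile Section XIII and the DSMB charter with Section VI, so that the numeric futility boundary on VAP recurrence appears in both as a non-binding guideline.

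The cost is wording, recomputed boundaries and slightly lower stated power: about one point under O'Brien-Fleming beta spending, more under aggressive beta spending. No patients are added. As a gauge, restoring the lost power would scale 458 to about 476-479 under O'Brien-Fleming beta spending, or 461-502 over the shapes examined.

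Stating the boundaries and declaring them compulsory in Sections XII and XIII would also remove the inconsistency without that loss of power, but alpha would then depend on the DSMB stopping at every crossing. The non-binding form protects alpha either way.
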